4 STUDY SCHEDULE

Enrolment process:

Study A: Participants will be identified through database screening (Renalware and PIMS/Electronic Patient Records) and approached in outpatient or wards by research specific staff and provided with a patient information sheet (PIS).

Study B: Participants will be identified and approached in outpatients by clinical staff and provided with a patient information sheet (PIS).

Participants who meet the inclusion and exclusion criteria for the study will not require any further screening prior to involvement in the study. Participant will provide written consent and samples taken for analysis.

Follow up: None, unless required following an Adverse Event. In such cases, the follow up will be as determined by the Principal Investigator.

Participant withdrawal criteria and procedures: If a participant wishes to withdraw their consent their information will be destroyed.

End of the study: The end of the study will occur after the final patient is recruited and final sample collection.

Table 1: Study A - Schedule of Assessments

	Pre Screening	Study Visit
Visit No		1
Informed Consent		X
Medical History		X
Vital Signs and lean body mass Bioimpedence		X
Eligibility confirmation	X	X
Concomitant Medication Review		X
Venous Serum Creatinine		X
POC-Cr		X
99mTc-DTPA		±2 days of POC-Cr
Or Biomarker panel		X
Adverse Events Review		X

Table 2: Study B - Schedule of Assessments

	Pre Screening	Baseline	Home Monitoring	Final Visit
Visit No		Day 1		Day 8
Window of flexibility for timing of visits:				Day 7-10
Informed Consent		X		
Medical History		X		
Vital Signs		X		
Eligibility confirmation	X	X		
Concomitant Medication Review		X		X
Venous Serum Creatinine		X		X
POC-Cr Health Care Professional		X		X
POC-Cr Patient		X	X	X
Test success reporting			X	
Adverse Events Review		X	X	X
SUTAQ Questionnaire				X

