STUDY SUMMARY

STUDY OVERVIEW	
Full title	Renal function Assessment with Point of Care creatinine In Diverse populations (RAPID)
Objectives	
Study A
 
 • To compare capillary POC-Cr with venous serum enzymatic creatinine concentrations (serum Cr) in people of different ethnicities performed by health care professionals and patients • To compare estimated glomerular filtration rate (eGFR) using POC-Cr and serum Cr with formal GFR assessment in people of different ethnicities • To define a threshold of POC-Cr concentration in different ethnicities which are confirmatory of eGFR <60mls/min/1.73m² (Kidney Disease Improving Global Outcomes; KDIGO Definition Stage 3) and a range of POC-Cr which may require further confirmation 
Study B
 
 • To conduct an observational cohort study of serial capillary self-testing POC-Cr for at least one week. • To compare single and serial capillary POC-Cr compared with single venous creatinine concentration IDMS traceable enzymatic assay • To assess test success rate, safety, training time, patient experience and acceptability of serial capillary POC-Cr testing
Type of trial	Two centre cross-sectional study and prospective longitudinal cohort study
Trial design and methods	
375 participants (including > 40 of African/African-Caribbean ancestry) having venous serum creatinine and 99mTc-DTPA nuclear medicine or venous GFR filtration panel testing will be recruited to a cross sectional study (Study A)
 
At least 40 patients with CKD will be recruited to a longitudinal study (Study B)
 
Demographics, medical and transportation details will be recorded
 
Finger-prick capillary creatinine will be assessed by POC-Cr device; Venous serum creatinine concentration (Isotope Dilution Mass Spectrometry (IDMS) Traceable Enzymatic assay).
 
Participants will be trained to use POC-Cr device, asked to self-monitor up to four times per day and report details including test failure and adverse events.
 
Patient experience and acceptability will be assessed using Service User Technology Acceptability Questionnaire.

Health condition(s) or problem(s) studied	Chronic Kidney Disease
Target sample size	At least patients 415 (Study A: 375; Study B: At least 40)
Trial duration per participant:	Study A: 1 Day Study B: 1 week

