2.2 Secondary Objectives

Study A

- To define a threshold of POC-Cr concentration in people of different ethnicities which are confirmatory of eGFR $<60\text{mls}/\text{min}/1.73\text{m}^2$ (Kidney Disease Improving Global Outcomes; KDIGO Definition Stage 3) and a range of POC-Cr which may require further confirmation.
- To compare capillary POC-Cr with venous serum enzymatic creatinine concentrations (serum Cr) in people of different ethnicities performed by health care professionals

Study B

- To assess test success rate, safety, training time, patient experience and acceptability of serial capillary POC-Cr testing

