Study A: POC-Cr will be assessed using the NovaMaxCreat and Epoc devices. Finger-prick capillary whole blood samples will be taken (0.05 uL for NovaMaxCreat and 0.9 uL for Epoc) using lancets by the research team. Venous serum creatinine for routine care (Isotope Dilution Mass Spectrometry (IDMS) Traceable Enzymatic assay) and ^{99m}Tc-DTPA glomerular filtration rate testing (where available) will be extracted from hospital laboratory databases. Participants not undergoing routine ^{99m}Tc-DTPA glomerular filtration rate testing will also have a 'eGFR filtration panel assessment – Beta-2-microglobulin, cystatin-C (processed by Synlab/ViaPath) and beta-trace-protein concentration (processed by Affinity laboratories), assessment on their venous blood sample.

Participants will be trained to use the POC-Cr device by the research team and time taken recorded and asked to perform one POC-Cr test.

In addition, the Epop Blood Analysis system, will also measure capillary potassium concentrations, which will be compared to serum potassium (taken from the venous blood sample for routine clinical care). This will be tested in the laboratory using the Roche Chemistry Analyser Cobas 8000.

Study B: Participants will be trained to use the POC-Cr device, NovaMaxCreat (NovaBio) by the research team and time taken recorded. Participants will be taught how to perform quality controls. All sample results will be digitally recorded by the device and downloaded after the device is returned. Participants will be asked to do one test at the hospital (with a simultaneous lab creatinine on site for validation), then to self-monitor four times per day (first thing in morning, midday, before evening meal/early evening, before bed) and each test recorded in a paper diary or electronically as desired. Details reported will include date and time of test, test success, device and non-device failures (test results, missed testing and reasons for missed test (e.g. forgot, did not want to test) and adverse events (e.g. pain or infection or prolonged injury after sampling, pre-syncopal or syncopal episode).

For participants who perform finger-prick testing for capillary blood glucose monitoring, both samples (creatinine using NovaMaxCreat and glucose using their usual device) can be taken from the same finger-prick test. However, participants will be advised to take the creatinine sample first.

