Participants will also be given the option to test more frequently or for longer than one week if desired and to report the reason for additional tests (concerned about previous result, demonstration for friend or family member). Reassurance will be given to participants about possibility of abnormal results and research team contact provided for discussion and repeat testing if desired of changes in results. Participants can have the opportunity (after consent) to trial self-testing on site, and decide if they wish to participate in self-monitoring at home.

Service User Technology Acceptability Questionnaire (SUTAQ): The SUTAQ questionnaire has been developed to measure the acceptability of telehealth and remote monitoring of chronic disease and includes assessment of quality of life, well-being, psychological processes and other patient-reported outcome measures (PROMs) which are evaluated with six acceptability scales: enhanced

care, increased accessibility, privacy and discomfort, care personnel concerns, kit as substitution and satisfaction.¹⁴ We have piloted the SUTAQ with minor adaptation developed with PPIE in our outpatient department. SUTAQ answers will be collected by the research team on tablet devices for Study B. Permission has been provided to use the SUTAQ by [name].

Samples (for Study A) will be sent to:

- i) Synlab UK - King's College Hospital NHS Foundation Trust (Cystatin C, Beta-2-microglobulin)
- ii) Affinity Biomarker Labs, [name] (beta-trace-protein)

The study sites and corresponding principal investigators are included in the table below.

Site	Study A and /or B	PI
King's College Hospital	A + B	[name]
Queen Alexandra Hospital, Portsmouth	B	[name]

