5 CONSENT

The participant must personally sign and date the latest approved version of the Informed Consent form before any of the study specific procedures are performed.

Written versions of the Participant Information and Informed Consent will be presented to the participants detailing the exact nature of the study, what it will involve for the participant, the implications and constraints of the protocol and any risks involved in taking part. It will be clearly stated that the participant is free to withdraw from the study at any time for any reason without prejudice to future care, and with no obligation to give the reason for withdrawal.

If he/she wishes to consider the information, the participant will be allowed as much time as he/she needs. He/she will be offered sufficient opportunity to question the Investigator, GP or other independent parties to decide whether he/she will participate in the study. Participants will not be rushed into making a decision. However, the convenience of the participant will also be considered including the right to immediate consent.

Written Informed Consent will then be obtained by means of participant dated signature and dated signature of the person who presented and obtained the Informed Consent. A member of the research team will go through the written information with the potential participant giving the opportunity for questions to be asked. Only researchers experienced in consent procedure and trained in Good Clinical Practice will take consent from participants.

In gaining consent from the participant we will ensure that the participant is able to:

1. Understand the purpose and nature of the research
2. Understand what the research involves including potential benefits and burden
3. Understand that the alternative to taking part is for them to receive standard medical care and that this is not affected by participation
4. Retain information long enough to make an effective decision
5. Make a free choice

The original signed form will be retained at the study site.

If there is any further safety information that may result in significant changes in the risk/benefit analysis, the PIS and Informed Consent Form (ICF) will be reviewed and updated accordingly. All

participants that are actively enrolled on the study will be informed of the updated information and given a revised copy of the PIS/ICF in order to confirm their wish to continue on the study.

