8 STATISTICAL METHODS

Study A: Readings taken with measured with NovamaxCreat and Epoc blood analysis system will be analysed separately. Bland-Altman plots and Passing-Bablok regressions will be generated for POC-Cr concentrations using Stata version 21 or later. The analytical error percentage compared to the reference standards (IDMS enzymatic traceable and 99mTc-DTPA and GFR filtration panel) ($=100 \times ([\text{POC device}] - [\text{reference standard}]) / [\text{reference standard}]$) will be calculated for each POC-Cr recording in each participant. In addition, average analytical error percentage and a 95% confidence interval (95%CI) will be calculated following Clinical Laboratory Standards Institute procedures.¹⁶ Criteria used to check analytical error percentage will be derived from the 'Desirable Specifications for Allowable Total Error (ATE)' database for creatinine (ATE=8,87%)¹⁵ and from the Laboratory Working Group of the National Kidney Disease Education Program (NKDEP) for eGFR (ATE=10%)¹⁷. Although the 10% ATE for eGFR is actually a performance specification for creatinine, it has been used in as an acceptable total error for eGFR.^{18,19,20} Categorical agreement of POC-Cr concentrations with the reference standards will be calculated using the unweighted Kappa statistic. Error analysis using predefined minor and major classification errors will be performed for POC-Cr concentrations. POC-Cr concentrations and reference standards will also be assessed by Deming regression and Pearson's correlation coefficient. Bias offset required will be recorded

Proportion of patients correctly identified to have CKD $eGFR < 60 \text{mls/min/1.73m}^2$ will be reported. Sensitivity and Specificity of different Cr thresholds calculated.

Study B: Number of tests attempted per participant, daily frequency of testing and proportion of successful attempts will be reported. Reasons for unsuccessful attempts and adverse events will be described and quantified if appropriate. Time taken to train per patient will be reported in minutes as median and IQR.

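### The only withdrawal rule destroys all of a participant's data and does not separate stopping self-testing from withdrawing permission to use data, so evidence on Study B's feasibility and safety objective can be lost

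*Protocol*

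**What the plan says.** Protocol section 4 (Study Schedule) has a single sentence on withdrawal: "If a participant wishes to withdraw their consent their information will be destroyed". Section 5 (Consent) tells participants that they are "free to withdraw from the study at any time for any reason without prejudice to future care, and with no obligation to give the reason". The protocol nowhere describes leaving the study while allowing data already collected to be used.

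The data at risk serve Study B's secondary objective in section 2.2: "To assess test success rate, safety, training time, patient experience and acceptability of serial capillary POC-Cr testing". After one test at the hospital, section 3 asks participants "then to self-monitor four times per day". Section 8 states the planned summary: "Number of tests attempted per participant, daily frequency of testing and proportion of successful attempts will be reported".

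Three other provisions matter here:

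- Section 3 (Study B) has participants log failures, adverse events, and missed tests with the reason, and not wanting to test is one of the example reasons. It also says: "Participants can have the opportunity (after consent) to trial self-testing on site, and decide if they wish to participate in self-monitoring at home".
- Section 14.3 requires all adverse events after consent to be recorded in the case report form. Section 14.4 requires serious events to be recorded in both the medical records and the case report form.
- Table 2 places the SUTAQ questionnaire at the final visit only (Day 8, window Day 7 to 10).

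**The concern.** In a study of whether patients can and will test themselves, a person who leaves because of pain, repeated failed tests, anxiety or burden is a result. Section 1 itself raises the possibility that self-monitoring increases anxiety. Followed as written, the rule in section 4 removes that person's attempts, failures, training time and recorded adverse events. No later analysis plan can recover destroyed records.

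Two things are at stake. First, if those who withdraw consent fared worse than those who stayed, the reported success rate is too high and the reported rate of non-serious adverse events is too low. Second, an adverse event that prompts withdrawal falls under two incompatible instructions: record it (section 14.3) and destroy it (section 4).

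A separate gap affects acceptability. Because the SUTAQ is given only at the final visit, anyone who stops before then has no score, even if none of their data are destroyed.

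**Working it through.** **What triggers destruction.** Reading sections 3, 4 and 14 together:

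| Participant | What the protocol provides |
|---|---|
| Skips tests or does not want to test | Stays in; missed tests and reasons are logged (section 3) |
| Tries on site, declines home testing | Not described as withdrawal, so nothing triggers destruction (section 3) |
| Stops early without withdrawing consent | Data kept, but no SUTAQ score unless seen at the final visit (Table 2) |
| Withdraws consent | All information destroyed (section 4) |
| Withdraws consent after a non-serious adverse event | To be recorded (section 14.3) and destroyed (section 4) |
| Withdraws consent after a serious adverse event | Also held in the medical records (section 14.4), which section 4 does not say are erased |

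**Size.** The protocol states no withdrawal rate, success rate or adverse event rate, so there is no figure of its own to reproduce. From the protocol come N = 40 (the minimum for Study B) and 4 tests × 7 days = 28 home tests per participant. The rest is assumed: d = 4, 6 or 8 withdrawers, 90% success in stayers and 40% in withdrawers.

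*Averaged per participant.* True rate = [(40 − d) × 0.90 + d × 0.40] / 40. The reported rate after destruction is 90%.

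- d = 4: (36 × 0.90 + 4 × 0.40) / 40 = 85%, overstated by 5 points
- d = 6: (34 × 0.90 + 6 × 0.40) / 40 = 82.5%, overstated by 7.5 points
- d = 8: (32 × 0.90 + 8 × 0.40) / 40 = 80%, overstated by 10 points

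*Pooled over attempts.* Assume that each stayer makes 28 attempts and each withdrawer makes 4 or 8 (1 or 2 days). Overstatement = (0.90 − 0.40) × withdrawer attempts / all attempts.

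| d | Stayer attempts | 1 day | 2 days |
|---|---|---|---|
| 4 | 36 × 28 = 1008 | 0.5 × 16/1024 = 0.8 points | 0.5 × 32/1040 = 1.5 points |
| 6 | 34 × 28 = 952 | 0.5 × 24/976 = 1.2 points | 0.5 × 48/1000 = 2.4 points |
| 8 | 32 × 28 = 896 | 0.5 × 32/928 = 1.7 points | 0.5 × 64/960 = 3.3 points |

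*Adverse events.* Assume that 10% of stayers have a non-serious event. Understatement = (d/40) × (proportion in withdrawers − 0.10).

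- Half of withdrawers affected: 4 points for d = 4 (true 14%), 8 points for d = 8 (true 18%)
- All withdrawers affected: 9 points for d = 4 (true 19%), 18 points for d = 8 (true 28%)

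If withdrawers and stayers have the same rates, every one of these differences is zero.

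**The case against.** The strongest reply is that the rule is narrow. Only withdrawal of consent triggers it, and section 3 captures failures, pain, missed tests and unwillingness to test in everyone who stays in. This stands. A reader might infer that success, safety and acceptability are estimated only in people who tolerated testing. The protocol does not support that: the results are conditional on not having withdrawn consent, which is a weaker condition than having completed or tolerated the week.

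The size is also unknown. Section 8 can be read as pooling over attempts, and people who leave early contribute few attempts, so the distortion may be only a point or two. This stands too.

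Serious events also go into the medical records, so they would not simply disappear. The safety concern is therefore mainly about non-serious events held as study data.

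Denominators and the counting of those who decline on site can be left to an analysis plan, and the information sheet is not available here. Both are fair. Neither answers the main point, because the destruction rule is stated in the protocol and its effect cannot be reversed at analysis.

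Finally, section 9 reports community concern about home surveillance and data ownership, which makes erasure a defensible option. It supports letting a participant ask for erasure. It does not require that leaving the study should automatically mean erasure.

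**Conclusion.** The concern holds in a limited form. Section 4 fixes one rule for leaving, and that rule erases evidence bearing directly on a stated Study B objective. It also contradicts section 14.3. Both faults exist whatever the size of any bias.

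Upward bias in success is a likely risk and not a demonstrated result. It requires withdrawers to do worse than stayers. Under the assumed 90% against 40% success with 4 to 8 withdrawers of 40, it is 5 to 10 points per participant or about 0.8 to 3.3 points per attempt, and zero if the groups do not differ. For non-serious adverse events the bias would run downwards.

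A reader might also infer that acceptability would look close to universal. The protocol does not support that: section 8 reports SUTAQ scale scores and not a proportion accepting. The missing scores of early stoppers come from the timing in Table 2 and not from the destruction rule.

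**What to change.** - Amend section 4 and the matching information-sheet wording so that stopping testing is separate from withdrawing permission to use data.
- By default, keep data collected up to the stop, including adverse events. Erase only on explicit request, and stay within what the participant consented to.
- Reconcile section 4 with sections 14.3 and 14.4, so that it is clear what happens to adverse event records when consent is withdrawn.
- Offer the SUTAQ at the point of stopping as well as at the final visit.
- Report how many stopped, withdrew or had data erased, against all consented Study B participants, with reasons where volunteered. Show those who declined home testing after the on-site trial explicitly.

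The cost is a short amendment to the protocol and information sheet. Success and acceptability figures may come out slightly less favourable. Participants will also need clear reassurance on data ownership, given the concerns in section 9.

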2 OBJECTIVES

2.1 Primary Objectives

Study A

- To compare estimated glomerular filtration rate (eGFR) using POC-Cr and serum Cr with formal GFR assessment in people of different ethnicities.

Study B

- To conduct an observational cohort study of serial capillary self-testing POC-Cr for at least one week.
- To compare capillary POC-Cr with venous serum enzymatic creatinine concentrations (serum Cr) in people of different ethnicities performed by health care professionals.
- To compare serial capillary POC-Cr compared with single venous creatinine concentration IDMS traceable enzymatic assay.

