3 STUDY DESIGN

Study A: Cross-sectional cohort study

Study B: Observational longitudinal cohort study

Research Ethics Committee approval and R&I approval will be sought for the study. Participants who meet the entry criteria will be recruited and consented by the investigator, or any GCP qualified member of the local research team who has delegated responsibility for study recruitment. Participants will be recruited from King's College Hospital, Royal London Hospital outpatients and wards and nuclear medicine department. Participants will be offered a minimum of 24 hours to reflect on the patient information sheet (PIS), which will be provided during initial discussion. Participants will be selected purposively to include a range of age, gender, ethnicity (at least 50% African/Afro Caribbean), severity of renal disease and clinical settings. Participants in study A will be able to participate in study B if they wish to do so.

Demographics, Body mass index, waist circumference and lean body mass (Fresenius - Body Composition Monitor and clinician estimated), mobility at home, mode of transportation to come to hospital, length and cost of travel, carer details, drug history, number of hospital visits and GP visits per year and reason for laboratory creatinine testing (e.g. monitoring Ig A nephropathy) will be recorded. Data will be transferred following pseudo-anonymisation into a study specific database by the research team.

POC-Cr testing

Capillary POC-Creatinine concentration will be assessed by NovaMaxCreat (NovaBio) and Epoc (Siemens) POC hand-held devices. A quality control will be performed for each POC-Cr device each day by the study nurse and by participants, ensuring the reagent batch conforms the manufacturers' quality specifications. POC reagents will be stored and used following manufacturers' specifications.

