6.2 Exclusion Criteria

- Unable or unwilling to give informed consent
- Any condition which would make finger prick contraindicated e.g. severe skin conditions, bleeding disorder
- Study A: If formal GFR testing has been requested only because estimated GFR is not considered to reflect true GFR (e.g. liver disease)

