7 RECRUITMENT

Patients who meet the entry criteria may be recruited and consented by the investigator, or any GCP qualified member of the local study team who has delegated responsibility for the study. Participants will be recruited from King's College Hospital, Royal London Renal Units and Nuclear Medicine Departments. Potential participants will be identified when presenting for their routine hospital clinic visits or during an inpatient admission. Members of the site staff will pre-screen and screen for potential eligible study participants using the inclusion/exclusion criteria.

Screening logs will be kept on the secure renal research study hard drive and will be encrypted for confidentiality. All eligible and ineligible patients, plus those declining to participate will be logged on the secure screening log. Patients who fulfil the inclusion criteria will have their eligibility confirmed by the research team. After confirming eligibility, eligible patients will be approached by an appropriately trained member of the clinic team to ascertain interest in entering the study. This individual will give a comprehensive verbal explanation of the study. Time for questions throughout the discussion will be given and questions adequately addressed. Potential participants will be given enough time to reflect on the patient information sheet (PIS), which will be provided during the initial discussion with the patient.

If the participant is willing to take part then they will be asked to sign the consent form with a member of the research team countersigning. A copy of the consent form will be given to the participant, and an electronic copy will be filed securely with the participant's records.

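### Study A can enrol patients on dialysis or with changing kidney function, whose eGFR may disagree with formal GFR even if creatinine is measured perfectly

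*Protocol*

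**What the plan says.** The primary objective of Study A (Protocol 2.1) is "To compare estimated glomerular filtration rate (eGFR) using POC-Cr and serum Cr with formal GFR assessment in people of different ethnicities". Section 8 computes a percentage error against each reference standard (venous enzymatic creatinine, DTPA and the filtration panel) and sets a 10% limit for eGFR.

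Recruitment is broad. Section 4 has Study A patients "approached in outpatient or wards by research specific staff". Section 7 says: "Potential participants will be identified when presenting for their routine hospital clinic visits or during an inpatient admission". It names as sources "King's College Hospital, Royal London Renal Units and Nuclear Medicine Departments". Section 3 selects purposively over, among other things, "severity of renal disease and clinical settings".

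Entry under 6.1 requires adulthood, willingness, and either a DTPA test or agreement to the panel. Section 6.2 has three exclusions: lack of consent, a contraindication to finger-prick, and "Study A: If formal GFR testing has been requested only because estimated GFR is not considered to reflect true GFR (e.g. liver disease". Section 4 asks for no screening beyond these criteria.

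On timing, Table 1 puts venous creatinine, POC-Cr and the panel at the single study visit. DTPA may fall within ±"2 days of POC-Cr".

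**The concern.** A creatinine-based eGFR describes GFR only when creatinine is in steady state. In someone whose kidney function is changing, or who is on dialysis, eGFR and formal GFR can differ without any measurement error. The Protocol accepts the principle, since 6.2 excludes some people whose eGFR is thought not to reflect true GFR. It then leaves two gaps.

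- Nothing in 6.1 or 6.2 addresses acute change or dialysis, although wards, inpatient stays and renal units are all recruitment sources.
- The 6.2 exclusion depends on the reason for a clinical request. A panel entrant has no such request, so a patient of the same kind is excluded by one route and admitted by the other.

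For DTPA participants, a gap of up to two days adds to the problem. At stake are the absolute agreement of eGFR with formal GFR, its comparison with the 10% limit and, if formal GFR is the classifier, sensitivity and specificity at 60.

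**Working it through.** **Inputs from the Protocol.** Window: 2 days either side (section 4, Table 1). Limit: 10% for eGFR, with error = 100 × (device − reference) / reference (section 8). The Protocol gives no share of unstable participants and no rate of change, so there is no stated figure to reproduce.

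**Assumptions for illustration.** Creatinine is measured without error. eGFR varies as creatinine to the power −1.2. GFR follows creatinine by the same relation. The last is a simplification, because creatinine lags behind GFR in acute change, so even a same-day pair can disagree.

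**Step 1: a creatinine rise of x between the two tests.**

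- POC-Cr first, DTPA later: error = (1 + x)^1.2 − 1
- DTPA first, POC-Cr later: error = (1 + x)^−1.2 − 1

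| Rise x | POC-Cr first | DTPA first |
|---|---|---|
| 25% | 1.307 − 1 = +31% | 0.765 − 1 = −23% |
| 50% | 1.627 − 1 = +63% | 0.615 − 1 = −39% |
| Rise that uses the 10% limit | 1.10^(1/1.2) − 1 = 8.3% | 0.90^(−1/1.2) − 1 = 9.2% |

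**Step 2: the same check in terms of GFR.** If GFR falls by g per day and DTPA follows POC-Cr by two days, the error is 1/(1 − g)² − 1. For g of 1%, 2%, 5% and 10% this gives +2.0%, +4.1%, +10.8% and +23.5%. If GFR rises at those rates, 1/(1 + g)² − 1 gives −2.0%, −3.9%, −9.3% and −17.4%. About 5% per day is enough to reach the limit.

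**Step 3: effect on the whole sample.** Assume an unstable share f of 10%. The answer depends heavily on the scatter among stable participants, so two cases are shown.

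- *Narrow scatter*, SD 10%/1.96 = 5.1%, so that 5.0% of stable results lie beyond ±10%. With a 20% discrepancy in the unstable group, 97.5% of that group lie beyond the limit. Overall: 0.90 × 5.0% + 0.10 × 97.5% = 14.3%. The half-width of the limits of agreement goes from 10% to 1.96 × √(5.1² + 0.10 × 20²) = 15.9%. With f of 5% or 20%, the share beyond ±10% is 9.6% or 23.5%.
- *Wide scatter*, SD 15%, to allow for error in the estimating equation. Already 50.5% of stable results lie beyond ±10%. Adding 10% of participants with discrepancies of ±25% or ±40% raises this only to 54.0% or 55.2%. The SD goes to √(15² + 0.10 × 25²) = 17.0% or √(15² + 0.10 × 40²) = 19.6%, so the limits of agreement widen by 13% or 31%.

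**Step 4: what is not touched.** POC-Cr and serum creatinine are both taken at the visit, so their comparison does not involve GFR or the DTPA date. The panel is also drawn at the visit, so the window has no effect on panel participants. They are exposed only through the missing eligibility rule.

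**The case against.** Several objections are sound and limit the point.

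- *Device error stays separable.* A reader might infer that the instability would be mistaken for device inaccuracy. The Protocol does not support this. Section 2.1 compares eGFR from both POC-Cr and serum creatinine with the same formal GFR, and 2.2 compares POC-Cr with venous creatinine directly. Instability moves both eGFRs in the same way.
- *The threshold at 60 may be unaffected.* Sections 2.2 and 8 define the target as eGFR below 60 and do not name measured GFR as the classifier. If eGFR from same-visit serum creatinine is the classifier, neither instability nor the window matters there.
- *Dialysis patients are not shown to be enrolled.* Recruiting in renal units does not mean recruiting dialysis patients, and the Study Summary names chronic kidney disease as the condition studied. The criteria permit such enrolment and do not call for it.
- *An ethnic difference is only conditional.* A spurious one would need unstable participants to be spread unevenly over ethnic groups, and the Protocol says nothing on that.
- *Breadth is intended, and analysis sets commonly belong in the SAP.* Section 3 does seek varied severity and settings, and an SAP not shown here might restrict the analysis. But eligibility and visit windows are Protocol content, and a later restriction needs stability to be defined and retrievable. The route-dependent exclusion is a flaw in the Protocol wording itself.

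**Conclusion.** The point holds as a design weakness of the primary eGFR-versus-formal-GFR comparison. As written, the criteria could admit participants with acutely changing creatinine or on dialysis. They also treat similar patients differently by route, and they allow a DTPA gap in which a modest change in kidney function uses up the 10% limit: a creatinine rise of about 8% if POC-Cr comes first, about 9% if DTPA comes first.

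The size in this study is unknown. It rests on the unstable share, which the Protocol does not give, and on the background scatter. The assumed cases run from a large effect (5.0% to 14.3% of results beyond the limit) to a small one (50.5% to 54.0%). If nearly all participants are stable outpatients, little changes. The documents do not support a claim that the POC-Cr versus serum comparison is compromised, or that the threshold or ethnic comparisons are necessarily distorted. The change is worth making because it is specific and cheap.

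**What to change.** 1. For the eGFR-versus-formal-GFR analysis, and for any threshold judged against formal GFR, restrict to participants who are not on dialysis and whose creatinine is not acutely changing. Define the latter by a prespecified rule (percentage change and look-back period, for the sponsor to set) based on prior routine results in the hospital database.
2. Record the interval between DTPA and POC-Cr. For inpatients, use only same-day DTPA pairs in that analysis.
3. Keep every participant in the POC-Cr versus same-visit venous creatinine comparison, which does not need steady state.
4. Reword the third exclusion in 6.2 and the Study Summary as a condition of the participant, applying equally to DTPA and panel entrants.

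The cost is a wording amendment, a look-up of prior creatinine results, and a somewhat smaller eGFR-versus-GFR set. The look-up is extra work: section 3 describes extracting the routine venous creatinine and DTPA results, not a serial history. Version 8.0 is dated 29 October 2024 and the study is due to end on 30/06/2025, so an eligibility change would reach few new participants. Items 1 to 3 work as analysis rules for those already enrolled, provided that prior results and test dates can be retrieved.
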